4.4.1.2 Unsolicited Non-serious AEs

4.4.1.2.1 Presence

An observation will be considered an event if it has at least a verbatim term and is not a Grade 0 intensity event. Grade 0 events should be included in the listing “Unsolicited non-serious adverse events not included in the safety analysis.”

4.4.1.2.2 Intensity

Intensity for unsolicited non-serious AEs will be derived according to the following classification: None, Grade 1, Grade 2, Grade 3, or Missing.

If the unsolicited non-serious AE is measurable and its preferred term (PT) is part of the list of solicited reactions, then the measurement is derived based upon and following the same rule as the intensity scales defined in the protocol for that measurable injection site or systemic reaction. Note the intensity could be considered “None” (not a reaction) in the analysis despite being considered a reaction by the investigator (e.g., swelling measurement > 0 mm but < 25 mm in adults).

Intensity for the other unsolicited non-serious AEs will correspond to the value reported in the (electronic) case report form (CRF).

The maximum intensity corresponds to the highest intensity for a unique term.

4.4.1.2.3 Last Vaccination

Last vaccination before an unsolicited non-serious AE is derived from the visit numbers provided in the clinical database and is calculated as follows:

- If an unsolicited non-serious AE has a non-missing visit number, the visit number should be used to determine the last vaccination before the unsolicited non-serious AE
- If the visit number is missing, then the start date of the unsolicited non-serious AE should be used to determine the last vaccination before the unsolicited non-serious AE

4.4.1.2.4 Time of Onset

Time of onset is derived from the start date of the unsolicited non-serious AE provided in the clinical database and the date of last vaccination:

- start date of the unsolicited non-serious AE – date of previous vaccination

The time of onset should be considered as missing only if 1 or both of the dates are missing or partially missing.

An AE with missing time of onset will be considered to have occurred just after the vaccination indicated by the visit number and will be included in these tables. For subjects who received 2 doses, the worst-case scenario will be used for the post-any dose summary (i.e., the shorter time to onset period will be used if present for both doses or the available time to onset period will be used if present for either dose).

Note: Unsolicited non-serious AE that occurred before vaccination (negative time of onset) will not be included in analysis, but will be listed separately.

Time of onset will be displayed as follows:

- D0–D3
- D4–D7
- D8–D14
- \geq D15
- Missing

4.4.1.2.5 Duration

Duration is derived from the start and stop dates of the unsolicited non-serious AE provided in the clinical database:

- stop date of unsolicited non-serious AE - start date of unsolicited non-serious AE + 1.

The duration should be considered as missing only if 1 or both of the start and stop dates of the unsolicited non-serious AE is missing or partially missing. For subjects who received 2 doses, the worst-case scenario will be used for the post-any dose summary (i.e., the longer duration will be used if present for both doses or the available duration will be used if present for either dose).

Duration will be displayed by period as following:

- 1–3 days
- 4–7 days
- 8–14 days
- \geq 15 days
- Missing

4.4.1.3 SAEs

4.4.1.3.1 Last Vaccination

Last vaccination before an SAE is derived from the visit number provided in the clinical database and is calculated as follows:

- If an SAE has a non-missing visit number, the visit number should be used to determine the last vaccination before the SAE
- If the visit number is missing, then the start date of the SAE should be used to determine the last vaccination before the SAE

4.4.1.3.2 Time of Onset

Time of onset will be computed using the same methodology as for unsolicited non-serious AEs described in Section 4.4.1.2.4.

An SAE with missing time of onset will be considered to have occurred just after the vaccination indicated by the visit number, so will be included in these tables.

Note: SAEs that occurred before initial vaccination with study vaccine (negative time of onset) will not be included in analysis, but will be listed separately.

4.4.1.3.3 Duration

Duration will be computed using the same methodology as for unsolicited non-serious AEs described in Section 4.4.1.2.5.

4.4.1.4 Other Safety Endpoints

4.4.1.4.1 Pregnancy

This information will be summarized as collected. No derivation or imputation will be done.

4.4.1.4.2 Action Taken

This information will be summarized as collected, including missing observations. No derivation or imputation will be done.

4.4.1.4.3 Seriousness

This information will be summarized as collected. No derivation or imputation will be done.

4.4.1.4.4 Outcome

This information will be summarized as collected. No derivation or imputation will be done.

4.4.1.4.5 Causality

This information will be summarized as collected. An adverse reaction (AR) is defined as an unsolicited non-serious AE or an SAE with causality to the vaccine. Missing causality (relationship) will be handled as described in Section 5.3.1.2.

4.4.1.4.6 AEs Leading to Study Discontinuation

A flag is available in the clinical database for all AEs in order to identify AEs leading to discontinuation.

In general, the items that are counted are:

- Disposition table: A subject who has, on the termination form, the reason for early termination “Serious Adverse Event” or “Other adverse event” is checked
- Safety overview table: A subject who has either on the termination form, the reason for early termination “Serious Adverse Event” or “Other adverse event” is checked or lists an AE on an AE page (solicited, unsolicited, or SAE) that has “Reaction Leading to Termination” or “Event Leading to Termination” or “Serious Adverse Event Leading to Termination” checked that is at least Grade 1 and is within the time period indicated
- SOC/PT table: An event (solicited, unsolicited, or SAE) that has “Reaction Leading to Termination” or “Event Leading to Termination” or “Serious Adverse Event Leading to Termination” checked that is at least Grade 1 and is within the time period indicated

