5.2.10 Classification of Subjects Who Discontinue the Study

For any subject who discontinues the study prior to completion, the most significant reason for early termination will be checked in the CRB. Reasons are listed below from the most significant to the least significant (refer to the CRB completion instructions for additional details and examples):

Adverse Event	To be used when the subject is permanently terminated from the study because of an AE (including an SAE), as defined in Section 9.3.1.1 . This category also applies if the subject experiences a definitive contraindication that is an SAE or AE.
Lost to Follow-up	To be used when the subject cannot be found or contacted in spite of efforts to locate him/her before the date of his/her planned last visit, as outlined in Section 5.2.9 . The certified letter was sent by the Investigator and returned unsigned, and the subject or parent/guardian did not give any other news and did not come to any following visit.
Protocol Deviation	To be used: 
• In case of significant noncompliance with the protocol (e.g., deviation of the Inclusion/Exclusion criteria, non-compliance with time windows, blood sampling or vaccination refusal, missed injection/treatment, or error in the vaccine/treatment administration).• If the subject experiences a definitive contraindication that is a protocol deviation.• The subject or the parent/guardian signed the certified letter sent by the Investigator but did not give any other news and did not come to any following visit.
Withdrawal by Subject or Parent/Guardian/Legally Acceptable Representative	To be used: 
• When the subject or parent/guardian indicated unwillingness to continue in the study• When the subject or parent/guardian made the decision to discontinue participation in the study for any personal reason other than an SAE/AE (e.g., subject is relocating, informed consent withdrawal)

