5.3.1.4 Intensity

For solicited reactions, missing intensities will be handled as described in Section 4.4.1.1.1. For unsolicited non-serious AEs, missing intensities will remain missing and will not be imputed.

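### The Grade 1 minimum in SAP 4.4.1.4.6 drops ungraded AEs that led to termination from the SOC/PT discontinuation table, and the SAP's termination-reason labels differ from the protocol's

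*SAP*

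**What the plan says.** SAP 4.4.1.4.6 gives three separate counting rules for AEs leading to discontinuation.

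- **Disposition table:** a subject for whom "the reason for early termination “Serious Adverse Event” or “Other adverse event” is checked". There is no grade condition.
- **Safety overview:** this opens "A subject who has either on the termination form, the reason for early termination" and offers an alternative route, an event on an AE page flagged as leading to termination "that is at least Grade 1 and is within the time period indicated".
- **SOC/PT table:** the flagged event only, under the same Grade 1 and time-period condition. The termination form plays no part.

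For unsolicited non-serious AEs, SAP 4.4.1.2.1 states: "An observation will be considered an event if it has at least a verbatim term and is not a Grade 0 intensity event". On the grade of those AEs, SAP 5.3.1.4 says that "missing intensities will remain missing and will not be imputed".

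Protocol 5.2.10 says that "the most significant reason for early termination will be checked in the CRB" and then lists four reasons. One of them, *Adverse Event*, concerns AEs, and its definition begins "To be used when the subject is permanently terminated from the study because of an AE (including an SAE". Protocol 5.2.8 uses the same single label for voluntary withdrawal over safety concerns.

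**The concern.** The SAP uses two different tests for whether an unsolicited AE counts. The AE tables exclude Grade 0, so an ungraded event stays in. The discontinuation filter demands a grade of 1 or more, so the same event falls out. The SAP's other conventions for incomplete records go the opposite way: SAP 5.3.1.2 treats missing causality as related, and SAP 5.3.1.5 keeps AEs with missing onset in the analysis.

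Whether an event led to early termination is part of four of the five safety endpoints in protocol 9.3.1.2 (items 2 to 5). The study is purely descriptive, so these counts are the result. They are likely to be at or near zero, where a single omission decides whether a group shows any discontinuation at all.

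The reason labels are a second, separate matter. The SAP names *Serious Adverse Event* and *Other adverse event*. Neither is in the protocol's list, and the SAP gives no mapping.

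**Working it through.** The plan has no figure to reproduce here, because the point concerns a counting rule. The check sets the rules side by side, runs them on example subjects, and sizes one missed case.

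**1. What the filter does to an ungraded event, by type**

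- *Solicited reactions.* SAP 4.4.1.1.3 already defines presence as Grade 1, 2 or 3. The Grade 1 minimum agrees with that, so there is no conflict.
- *Unsolicited non-serious AEs.* Under SAP 4.4.1.2.1 an ungraded AE is an event. Under SAP 5.3.1.4 its grade stays missing, and a missing grade cannot meet a Grade 1 minimum. The two rules conflict.
- *SAEs.* SAP 4.4.1.4.6 names SAEs in the filter, and protocol 9.3.1.3.3 has intensity recorded for serious and non-serious unsolicited AEs. SAP 4.4.1.3 has no intensity derivation for SAEs, and SAP 5.3.1.4 covers only solicited reactions and unsolicited non-serious AEs. An ungraded SAE fails the filter, and no other rule covers it.

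**2. The three rules applied to example subjects**

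Each subject has an unsolicited AE flagged as leading to termination, within the period. *Mapped* takes the protocol's *Adverse Event* as equivalent to the SAP's two labels. *Literal* does not.

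| Recorded reason | Grade | Reading | Disposition | Overview | SOC/PT |
|---|---|---|---|---|---|
| Adverse Event | 2 | mapped | yes | yes | yes |
| Adverse Event | 2 | literal | no | yes | yes |
| Adverse Event | missing | mapped | yes | yes | **no** |
| Adverse Event | missing | literal | no | no | no |
| Withdrawal | 2 | either | no | yes | yes |
| Withdrawal | missing | either | **no** | **no** | **no** |

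With the labels mapped, two gaps remain. An ungraded event is lost from SOC/PT, and an ungraded event with a non-AE reason is lost from all three tables. If missing intensity were allowed to count, row 3 would become yes in all three tables. Row 6 would become yes in the overview and SOC/PT.

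**3. Size of one missed case**

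Inputs: planned groups of 30 and 60 (SAP 5.5) and exact Clopper-Pearson two-sided 95% intervals (SAP 5.1.3.1).

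- Upper limit for 0/n is 1 − 0.025^(1/n). For n = 30 this is 11.6%, and for n = 60 it is 6.0%.
- Upper limit for 1/n is the 0.975 quantile of Beta(2, n − 1). For n = 30 this is 17.2%, and for n = 60 it is 8.9%.

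| n | True count reported | One case missed |
|---|---|---|
| 30 | 1/30 = 3.3% (0.1 to 17.2) | 0/30 = 0% (0 to 11.6) |
| 60 | 1/60 = 1.7% (0.04 to 8.9) | 0/60 = 0% (0 to 6.0) |

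These figures show the consequence of a missed case. They say nothing about how probable one is.

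**The case against.** The strongest reply is that an ungraded AE which ended participation should hardly ever reach database lock. Protocol 5.1.4 requires follow-up of any AE that caused discontinuation. Protocol 9.3.1.3.3 requires an intensity for every unsolicited AE. Protocol 11.1 makes investigators explain missing information, 11.2 applies consistency checks, and 13.4.1 closes all queries before lock. SAP 5.6 adds a statistical review. Protocol 5.2.10 also ranks *Adverse Event* first among the reasons, so a flagged AE with another recorded reason is a discrepancy that a query should catch. All of this stands. It makes the case rare, but it does not make the two rules agree.

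The tables need not match exactly either. Disposition counts subjects by one principal reason, while SOC/PT counts flagged events. That also stands, but it does not explain losing an event solely because its grade is blank.

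Three stronger readings are tempting, and the documents do not support them.

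- *The Disposition count of AE terminations will be zero.* That follows only if the labels are applied literally. The SAP's two labels read naturally as a split of the protocol's category, which includes SAEs. The CRB termination form is not among the documents, so the mismatch is shown against the protocol's list and not against the form.
- *A discontinuation must pass both the reason test and the grade test.* It need not. Disposition has no grade test, the overview accepts either route, and only SOC/PT rests wholly on the grade.
- *Adult redness or swelling under 25 mm is wrongly dropped.* Grading it None is deliberate: it follows protocol Table 9.3, and SAP 4.4.1.1.1, 4.4.1.1.7 and 4.4.1.2.2 say so, with adult swelling as the example. Counting such a reaction here would contradict the reaction tables.

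**Conclusion.** The point holds for ungraded unsolicited AEs and SAEs that are flagged as leading to termination. For non-serious AEs, the SAP's own event definition conflicts with its discontinuation filter. For SAEs, the rule for missing intensity is absent. The lasting effect is on the SOC/PT table and the AE-page route of the overview. Disposition and overview are sound for every subject whose recorded reason is an AE, provided that the labels are mapped. The label difference is real but is a matter of alignment.

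The effect is small and descriptive, and few subjects, if any, would be affected. The interval figures assume groups at their planned size and exactly one true case, which is missed. The correction is worth making because it costs almost nothing and the counts concerned are close to zero.

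**What to change.** In SAP 4.4.1.4.6:

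1. For unsolicited AEs and SAEs, replace the Grade 1 minimum with *not Grade 0/None; missing intensity counts*, in both the overview's AE-page route and the SOC/PT table. This also supplies the missing SAE rule for these tables.
2. Replace the two termination reasons with the protocol's *Adverse Event*, split by the serious flag on the AE form. Check the wording against the CRB termination form.
3. List separately, without counting, any solicited reaction flagged as leading to termination whose derived grade is None. SAP 4.4.1.2.1 already provides a listing for Grade 0 unsolicited non-serious AEs.
4. Before lock, reconcile the three tables subject by subject, and query any flagged AE that has no grade or a non-AE termination reason.

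The cost is SAP wording, the matching program condition and one listing. No new data are needed, and the protocol does not change.

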4.4.1.4.7 AEs of Special Interest

Adverse events of special interest (AESIs) will be captured as SAEs. These include new-onset of Guillain-Barré syndrome (GBS), encephalitis/myelitis (including transverse myelitis), neuritis (including Bell’s palsy, optic neuritis, and brachial neuritis), thrombocytopenia, vasculitis, convulsions (including febrile convulsions [children only]), and anaphylaxis or other hypersensitivity/allergic reactions from Visit 1 through Visit 2 for subjects receiving 1 dose of vaccine, or from Visit 1 through Visit 3 for subjects receiving 2 doses of vaccine.

4.4.2 Immunogenicity

4.4.2.1 Computed Values for Analysis

To appropriately manage extreme values ($< \text{LLOQ}$ [lower limit of quantification] and $\geq \text{ULOQ}$ [upper limit of quantification]) for analysis purposes, the following computational rule will be applied to the values provided in the clinical database for each BL (blood sample) drawn:

In order to appropriately manage replicate values for analysis purposes, the individual GM of all values will be computed for each BL after managing extreme values as described:

- If a value is $< \text{LLOQ}$, then the computed value $\text{LLOQ}/2$ will be used
- If a value is between $\geq \text{LLOQ}$ and $< \text{ULOQ}$, then the value will be used
- If a value is $\geq \text{ULOQ}$, then the value ULOQ will be used

4.4.2.2 Seroprotection

If the computed value is ≥ 40 (1/dilution [dil]) at pre-vaccination or at post-final vaccination (28 [window, 28–35] days following the final vaccination for subjects 6 months to < 9 years of age; and 21 [window, 21–28] days post-vaccination for subjects ≥ 18 years of age), then the derived seroprotection indicator will be “Yes” for that test, otherwise seroprotection will be “No”. Note: If the computed value is missing, seroprotection will be missing.

4.4.2.3 Fold-rise

The derived endpoint fold-rise is driven by both baseline and post-baseline computed values and is computed as follows. Generally, for extreme values, this algorithm minimizes the numerator and maximizes the denominator.

- If the baseline computed value is < LLOQ and the post-baseline computed value is < LLOQ then the fold-rise is 1
- If the baseline computed value is \geq LLOQ and the post-baseline computed value is \geq LLOQ then the fold-rise is post-baseline computed value / baseline computed value
- If the baseline computed value is \geq LLOQ and the post-baseline computed value is < LLOQ then the fold-rise is (LLOQ/2)/baseline computed value
- If the baseline computed value is < LLOQ and the post-baseline computed value is \geq LLOQ then the fold-rise is post-baseline computed value / LLOQ

Note: If baseline or post-baseline is missing, then fold-rise is missing.

4.4.2.4 Seroconversion

If a pre-vaccination titer is < 10 (1/dil) and a post-final vaccination titer is ≥ 40 (1/dil), or a pre-vaccination titer is ≥ 10 (1/dil) and there is a ≥ 4 -fold increase in post-final vaccination titer, then the derived seroconversion indicator will be “Yes” for that test, otherwise seroconversion will be set to “No”.

4.4.3 Efficacy

Not applicable

4.4.4 Derived Other Variables

4.4.4.1 Age for Demographics

The age of a subject in the study is collected as the calendar age in months for children under 2 years old, and in years for subjects 2 years and older at the time of inclusion. The calendar age is the age computed automatically in the CRF, and presented as an integer.

4.4.4.2 Duration of a Subject in the Trial

The duration of a subject in the study is computed as follows:

Maximum (date of visit, date of termination form) - (date of visit 1 of that subject) + 1

4.4.4.3 Duration of the Study

The duration of the study is computed in days as follows:

Maximum of all subjects (date of last visit, date of termination form) - minimum for all subjects (date of Visit 1) + 1.

5 Statistical Methods and Determination of Sample Size

The statistical analyses will be performed under the responsibility of the Sponsor’s Biostatistics platform using SAS® Version 9.4 software or later.

The results of the statistical analysis will be available in the final clinical study report (CSR).

For descriptive purposes, the following statistics will be presented:

Table 5.1: Descriptive statistics produced

Baseline characteristics and follow-up description	Categorical data	Number of subjects. Percentage of subjects.
	Continuous data	Mean, standard deviation (SD), quartiles, minimum, and maximum.
Clinical safety results	Categorical data	Solicited: Number and percentage (95% CIs) of subjects. Unsolicited: Number and percentage (95% CIs) of subjects, and number of events.
Immunogenicity results	Categorical data (seroprotection, seroconversion, cutoff)	Number and percentage (95% CIs) of subjects.
	Continuous data (titer / data†)	Log10: Mean and standard deviation. Anti-Log10 (work on Log10 distribution, and anti-Log10 applied): Geometric mean (GM), 95% CI of the GM, quartiles, minimum, and maximum. Graphical representation by a reverse cumulative distribution curve (RCDC).

The confidence interval (CI) for the single proportion will be calculated using the exact binomial method (Clopper-Pearson method, quoted by Newcombe (8), i.e., using the inverse of the beta integral with SAS®).

For immunogenicity results, assuming that Log_{10} transformation of the titers/data follows a normal distribution, at first, the mean and the 95% CI will be calculated on Log_{10} (titers/data) using the usual calculation for normal distribution (using Student's t distribution with n-1 degree of freedom), then antilog transformations will be applied to the results of calculations, in order to provide geometric means and their 95% CI.

5.1 Statistical Methods

Summaries of baseline demographic characteristics of the study subjects will be presented. The number of subjects enrolled and their age at enrollment (mean, median, and minimum and maximum), sex, race, and ethnic origin will be summarized, along with the number and description of protocol deviations.

5.1.1 Hypotheses and Statistical Methods for Primary Objectives

There are no primary objectives for this study.

5.1.2 Hypotheses and Statistical Methods for Secondary Objectives

There are no secondary objectives for this study.

5.1.3 Statistical Methods for Observational Objectives

For the main safety and immunogenicity parameters, 95% CIs of point estimates of proportions will be calculated using the normal approximation for quantitative data and the exact binomial distribution (Clopper-Pearson method) for proportions.

5.1.3.1 Safety

All analyses will be descriptive; no hypotheses will be tested.

The safety analysis will report the occurrence of solicited reactions and the incidence of unsolicited AEs between Visit 1 and Visit 2 (or between Visit 1 and Visit 3 for those subjects receiving 2 doses).

The number of subjects with documented safety will be used as denominator for the frequencies.

- For solicited reactions, the denominator will be the total number of subjects who have non-missing data for the endpoint considered
- For unsolicited AEs, the denominator will be the total number of subjects who were vaccinated with the dose analyzed

The safety tables will be produced using a subject approach; i.e., number of subjects who experienced at least 1 safety event during a considered period.

The 2-sided 95% CIs for the percentages will be calculated using the exact binomial method (Clopper-Pearson method).

Solicited reactions

The solicited injection site reactions and the solicited systemic reactions will be presented separately (except in summary tables).

Solicited reactions will be presented according to their nature (Medical Dictionary for Regulatory Activities [MedDRA, the latest version at database lock] PT), intensity (Grade 1, 2, or 3), time to onset, and number of days of occurrence.

Unsolicited AEs

Unsolicited AEs included in the analysis will be summarized in the safety overview and analyzed according to their nature (MedDRA [the latest version at database lock] system organ class [SOC] and PT classification) and relationship to the vaccination.

Injection Site Reactions

For each treatment group, the number and percentage of subjects experiencing any injection site reaction after injection will be calculated.

The description of injection site reactions will be presented according to:

- Solicited injection site reactions
All solicited injection site reactions that occur each day within 7 days after injection will be analyzed.
- Unsolicited injection site reactions
All unsolicited injection site reactions between Visit 1 and Visit 2 (or between Visit 1 and Visit 3 for those subjects receiving 2 doses) will be described according to the type of events.

Systemic Events and Reactions

For each treatment group, the number and percentage of subjects experiencing any unsolicited immediate systemic event in the 20 minutes after injection will be calculated.

In addition, the description of systemic events will be structured according to:

- Solicited systemic reactions
- All solicited systemic reactions that occur each day within 7 days after injection will be analyzed.
- Unsolicited systemic events
All unsolicited systemic events between Visit 1 and Visit 2 (or between Visit 1 and Visit 3 for those subjects receiving 2 doses) will be described according to the type of events.

Serious Adverse Events

The number and percentage of subjects with SAEs after vaccination between Visit 1 and Visit 2 (or between Visit 1 and Visit 3 for those subjects receiving 2 doses) in each treatment group will be calculated by outcome, seriousness, and relationship to vaccination.

